5.2 EXPLORATORY (EFFICACY) ENDPOINTS

There are several exploratory endpoints. In order to preserve the alpha level these will be tested hierarchically in the order presented here. Each endpoint along with the analysis method and SAS procedure to analyze the data is presented.

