3.2.2 Secondary Objectives

The secondary trial objectives evaluate the efficacy of inhaled Ampion versus placebo control in improving the clinical course and outcomes of participants with prolonged respiratory complications after a COVID-19 infection.

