9.4.2 Exploratory Endpoints

Exploratory efficacy endpoints assess the effect of inhaled Ampion compared to placebo on the clinical outcomes for participants with prolonged respiratory complications after a COVID-19 infection per [Section 3.3.2](#).

The efficacy endpoints will be evaluated to estimate the treatment effect and use descriptive statistics including mean, standard deviation, percentages, minimum/maximum, and 95% confidence intervals. All endpoints will be tabulated and presented by treatment arm, cohort

(moderate and severe), and timepoint. Where appropriate, data will be tabulated and presented cumulatively across cohorts and/or timepoints.

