2.2.2 Secondary Objective

The exploratory trial objectives evaluate the efficacy of inhaled Ampion versus placebo control in improving the clinical course and outcomes of participants with prolonged respiratory complications after a COVID-19 infection.

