5.2.1 Assess the effect of Ampion compared to placebo on symptom improvement

- Change in FDA Assessment of 14 Common COVID-19-Related Symptoms questionnaire from baseline to Day 7; Day 28; Day 60

The hypotheses to be tested are:

$$H_0: \mu_A = \mu_S \text{ versus } H_A: \mu_A \neq \mu_S$$

Where μ_A and μ_S represent the score shift through day 7, 28, and 60 for Ampion and Placebo after randomization. The difference between Ampion and Placebo with respect to the percent change from baseline at day 7, 28, and 60 will be tested utilizing a Wilcoxon rank-sum test via PROC NPAR1WAY. To assess any potential time trends an exploratory repeated measures analysis of variance will be performed with terms for treatment, time and the interaction between the two. This will be done utilizing PROC GLM with the REPEATED option.

- Change in Borg Dyspnoea Scale (mBDS) from baseline to Day 7; Day 28; Day 60

The hypotheses to be tested are:

$$H_0: \mu_A = \mu_S \text{ versus } H_A: \mu_A \neq \mu_S$$

Where μ_A and μ_S represent the scale shift through day 7, 28, and 60 for Ampion and Placebo after randomization. The difference between Ampion and Placebo with respect to the percent change from baseline at day 7, 28, and 60 will be tested utilizing a Wilcoxon rank-sum test via PROC NPAR1WAY. To assess any potential time trends an exploratory repeated measures analysis of variance will be performed with terms for treatment, time and the interaction between the two. This will be done utilizing PROC GLM with the REPEATED option.

- Change in all-cause mortality

The hypotheses to be tested are:

$$H_0: \pi_A = \pi_S \text{ versus } H_A: \pi_A \neq \pi_S$$

Where π_A and π_S represent the all-cause mortality rates for Ampion and Placebo during the first 60 days after randomization.

The difference between Ampion and Placebo will be tested using the appropriate chi-square test or Fisher's exact test utilizing PROC FREQ with the EXACT option, if necessary

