10 CHANGES IN CONDUCT OF STUDY OR TO PLANNED ANALYSES FROM PROTOCOL

Deviations from the statistical analyses outlined in this plan will be indicated; any further modifications would be noted in the final statistical analyses.

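### SAP 5.2 replaces the protocol's estimation plan for efficacy with a testing hierarchy, does not declare the change, and specifies the hierarchy too loosely to preserve any alpha level

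*SAP*

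**What the plan says.** Protocol 9.4.2 describes the efficacy analysis as estimation: "The efficacy endpoints will be evaluated to estimate the treatment effect and use descriptive statistics". The list that follows includes 95% confidence intervals. It names no test, significance level or order of endpoints.

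SAP 5.2 treats the same endpoints differently: "In order to preserve the alpha level these will be tested hierarchically in the order presented here". SAP 5.2.1 to 5.2.3 then give null and two-sided alternative hypotheses for eight endpoints, in this order:

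1. 14-item symptom questionnaire
2. Borg dyspnoea scale
3. All-cause mortality
4. Blood oxygen saturation
5. Six-minute walk test
6. SF-36
7. Fatigue
8. Sleep disturbance

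Only chest imaging (SAP 5.2.4) stays descriptive. For the seven endpoints other than mortality, the "percent change from baseline at day 7, 28, and 60 will be tested utilizing a Wilcoxon rank-sum test via PROC NPAR1WAY". Mortality over 60 days is compared by a chi-square or Fisher's exact test.

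SAP section 10, whose heading covers changes from the protocol, contains one general sentence: "Deviations from the statistical analyses outlined in this plan will be indicated; any further modifications would be noted in the final statistical analyses". It speaks of departures from the SAP and lists no departure from the protocol.

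**The concern.** The two documents give different analysis plans for the same endpoints, and nothing tells the reader that the plan changed. SAP section 2 labels as post hoc only those analyses that the SAP does not specify, so the hierarchy would enter the report as prespecified.

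The stated purpose also matters. A fixed testing order offered "In order to preserve the alpha level" tells readers that a significant result carries a known error rate. That holds only if the alpha, the rule for passing each step and the consequence of a failure are all fixed in advance. If they are not, the sentence gives an assurance that the plan does not support. A step that can hardly be passed would also cut off every endpoint behind it, whatever the drug does.

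**Working it through.** **Inputs.** SAP section 4 gives 15 patients per arm. SAP 5.2.1 to 5.2.3 give the two-sided alternatives, the order of endpoints and the three days. Neither document states an alpha, so 0.05 is assumed throughout. No correlation between days is given, so a range is shown. There is no stated power or error figure to reproduce.

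**Number of tests.** 7 endpoints × 3 days + 1 mortality test = 22, counting each questionnaire as one score.

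**First step, the symptom questionnaire.** The SAP does not say whether the step is passed by one day, by all three, or by the days in sequence. Suppose any one day is enough:
- Independent days: 1 − (1 − 0.05)³ = 1 − 0.857 = 14.3%.
- Correlated days: simulating Wilcoxon tests with 15 per arm, normal outcomes and no treatment effect gives about 12% at correlation 0.5. At correlations of 0.3 and 0.7 it gives about 13% and 10%.

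Requiring all three days, or taking the days in a fixed sequence, would hold this step at or below 5%. The SAP states neither rule.

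**Third step, mortality.** If all D deaths fall in one arm, the two-sided Fisher p-value is 2 × C(15, D) / C(30, D).
- D = 4: 2 × 1,365 / 27,405 = 0.100.
- D = 5: 2 × 3,003 / 142,506 = 0.042.

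The smallest number of deaths that can reach significance is therefore five, all in one arm. An uncorrected chi-square test would give p = 0.032 at 4 against 0, but the expected count is then 2 deaths per arm. SAP 7.3 uses Fisher's test for baseline comparisons when an expected value is below 5, and the same convention would apply it here.

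The power of this step, by summing the binomial probabilities of all significant tables, is:
- 6.4% at 8% against 21%, the mortality that Protocol 2.3 reports for the earlier inhalation trial in severe COVID-19.
- 0.05% at 1% against 5%, assumed for illustration.

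This trial excludes patients who require hospitalization (Protocol 4.5), so the lower rates are the more plausible. If no one dies, the step cannot be passed. The chance of no deaths among 30 patients is (1 − rate)³⁰: 74% at a 1% rate, 55% at 2% and 21% at 5%.

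**Consequence.** If the sequence stops at the first failure, the five endpoints behind mortality (oxygen saturation, walk test, SF-36, fatigue and sleep) depend on a step with at most a few percent chance of passing under any rates in the documents or plausible here.

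**If all tests were run unadjusted.** With 22 independent tests at 0.05, the chance of at least one false positive is 1 − 0.95²² = 67.6%. Correlation would lower it. This is why nominal p-values need a clear label.

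**The case against.** Four arguments on the other side deserve weight.

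*The protocol does not forbid efficacy tests.* Protocol 9.4.2 does not say that the analysis is solely descriptive. Protocol 9.4.1 rules out statistical tests for adverse events in so many words, and no such sentence covers efficacy. Protocol 3.4 foresees a separate SAP, so adding tests there can be read as elaboration. This stands. It makes the fault one of undeclared difference rather than breach.

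*The SAP keeps the exploratory label.* A reader might infer that the hierarchy lets a 30-patient result be reported as formal proof, or formal failure, of efficacy. The documents do not support that. SAP 5.2 is headed exploratory, no passage plans an efficacy claim, and SAP sections 7 and 12 keep descriptive summaries that a failed step would not remove. SAP section 7 does not, however, expressly promise a confidence interval for the difference between arms.

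*Low power is not the point.* At 0.5 SD, a Wilcoxon test with 15 per arm has about 24% power. A t-based 95% interval would exclude zero about 26% of the time. That reflects the trial's size under either document.

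*A prespecified order limits selective emphasis.* This is true, and removing it is a real, if small, loss.

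A reader might also make much of the headings. The protocol places efficacy under secondary objectives ("The secondary trial objectives evaluate the efficacy of inhaled Ampion versus placebo control"), while the SAP puts exploratory wording under a secondary heading ("The exploratory trial objectives evaluate the efficacy of inhaled Ampion versus placebo control"). Both documents list the endpoints themselves as exploratory, so this is editorial.

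**Conclusion.** The concern holds as an undeclared difference between protocol and SAP, together with a hierarchy that lacks the property claimed for it. The textual conflict needs no assumption beyond the SAP text available, including the section where a declaration belongs. The first-step error of about 12% (up to 14.3%) rests on an assumed alpha of 0.05, on any one day sufficing, and on correlation 0.5 between days. The conclusion that five endpoints would almost certainly go untested rests on Fisher's test, 15 per arm, and stopping at the first failure, which is the usual meaning of a hierarchical order but is not spelled out in the SAP.

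The finding does not extend to a claim that the protocol prohibits testing, or that the sponsor plans a confirmatory efficacy claim. It concerns only the efficacy endpoints of a Phase I safety trial and should be corrected before any unblinded analysis.

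**What to change.** In SAP 5.2, delete the sentence that announces hierarchical testing to preserve alpha. State that every efficacy endpoint will be reported as a between-arm estimate with a 95% confidence interval, in line with Protocol 9.4.2. If p-values are kept, label them nominal, unadjusted for about 22 tests, and not a basis for an efficacy claim. Record in SAP section 10 that the tests are an addition to the protocol. The objective headings in Protocol 3.2.2 and SAP 2.2.2 can be aligned at the same time.

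If the sponsor prefers to keep a hierarchy, the SAP must state the alpha, the rule across the three days and what follows a failed step. It must also reconsider the position of mortality and declare the change in section 10.

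The recommended change is wording only and alters no procedure, visit or sample size. The cost is the loss of a fixed testing order and of any formal significance claim for efficacy.

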5.2.1 Assess the effect of Ampion compared to placebo on symptom improvement

- Change in FDA Assessment of 14 Common COVID-19-Related Symptoms questionnaire from baseline to Day 7; Day 28; Day 60

The hypotheses to be tested are:

$$H_0: \mu_A = \mu_S \text{ versus } H_A: \mu_A \neq \mu_S$$

Where μ_A and μ_S represent the score shift through day 7, 28, and 60 for Ampion and Placebo after randomization. The difference between Ampion and Placebo with respect to the percent change from baseline at day 7, 28, and 60 will be tested utilizing a Wilcoxon rank-sum test via PROC NPAR1WAY. To assess any potential time trends an exploratory repeated measures analysis of variance will be performed with terms for treatment, time and the interaction between the two. This will be done utilizing PROC GLM with the REPEATED option.

- Change in Borg Dyspnoea Scale (mBDS) from baseline to Day 7; Day 28; Day 60

The hypotheses to be tested are:

$$H_0: \mu_A = \mu_S \text{ versus } H_A: \mu_A \neq \mu_S$$

Where μ_A and μ_S represent the scale shift through day 7, 28, and 60 for Ampion and Placebo after randomization. The difference between Ampion and Placebo with respect to the percent change from baseline at day 7, 28, and 60 will be tested utilizing a Wilcoxon rank-sum test via PROC NPAR1WAY. To assess any potential time trends an exploratory repeated measures analysis of variance will be performed with terms for treatment, time and the interaction between the two. This will be done utilizing PROC GLM with the REPEATED option.

- Change in all-cause mortality

The hypotheses to be tested are:

$$H_0: \pi_A = \pi_S \text{ versus } H_A: \pi_A \neq \pi_S$$

Where π_A and π_S represent the all-cause mortality rates for Ampion and Placebo during the first 60 days after randomization.

The difference between Ampion and Placebo will be tested using the appropriate chi-square test or Fisher's exact test utilizing PROC FREQ with the EXACT option, if necessary

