4.4 Inclusion Criteria

Patients should fulfill all the following inclusion criteria:

1. Male or female adults: ≥ 18 years.
2. Must have a clinical diagnosis of COVID-19 at least 4 weeks prior to the screening date, with at least one of clinical symptoms (e.g., fever $\geq 38^{\circ}\text{C}$, fatigue, cough) and a positive result by the reverse-transcription polymerase chain reaction (RT-PCR) testing or equivalent.
3. Experiencing at least two COVID-19 respiratory symptoms with a score of two or higher using the FDA Assessment of 14 Common COVID-19-Related Symptoms questionnaire for at least 4 weeks (28 days) after initial positive COVID-19 diagnosis: cough, sore throat, runny/stuffy nose, shortness of breath (difficulties breathing), tightness of chest, low exercise tolerance.
4. Able to bear weight and ambulate a minimum of 10 meters distance.
5. Women of childbearing potential and their partner must agree to use at least one highly effective method of contraception (e.g., hormonal contraceptives [implants, injectables,

combination oral contraceptives, transdermal patches, or contraceptive rings], intrauterine devices, bilateral tubal occlusion, or sexual abstinence) for the duration of the study.

6. Informed consent obtained from the patient.

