2.3.2 Exploratory

Exploratory efficacy endpoints assess the effect of inhaled Ampion compared to placebo on the clinical outcomes for participants with prolonged respiratory complications after a COVID-19 infection as follows:

Objective	Endpoint
Assess the effect of Ampion compared to placebo on symptom improvement	
• Change in FDA Assessment of 14 Common COVID-19-Related Symptoms questionnaire from baseline to Day 7; Day 28; Day 60• Change in Borg Dyspnoea Scale (mBDS) from baseline to Day 7; Day 28; Day 60• Change in all-cause mortality
Assess the effect of Ampion compared to placebo on pulmonary function	
• Change in blood oxygen saturation from baseline to Day 7; Day 28; Day 60• Change in six-minute walk test (6MWT) score from baseline to Day 7; Day 28; Day 60
Assess the effect of Ampion compared to placebo on global impression	
• Change in Quality-of-Life Assessment using SF-36 from baseline to Day 7; Day 28; Day 60

	
• Change in Fatigue questionnaire from baseline to Day 7; Day 28; Day 60• Change in Sleep Disturbance questionnaire from baseline to Day 7; Day 28; Day 60
Assess the effect of Ampion compared to placebo on radiographic findings	
• Change in chest imaging on ground-glass opacity, local patchy shadowing, bilateral patchy shadowing, and/or interictal abnormalities from baseline to Day 60

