6.2.2 Intent-to-treat Population

The intent-to-treat (ITT) analysis population is defined as all randomized patients. All efficacy analyses will be performed in the ITT population. Patients will be analyzed as randomized.

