15.2 BORG DYSPNOEA SCALE

Borg Dyspnoea Scale will be conducted at baseline, Day 7, Day 28, and Day 60. This scale asks you to rate the difficulty of your breathing it starts at number 0 where you are breathing is causing you no difficulty at all and progresses through to number 10 where your breathing difficulty is maximal.

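### The Borg percent-change test is undefined for anyone with a baseline of 0, which entry allows and no rule covers; SAP 5.2.1 to 5.2.3 also plan no between-arm difference with a confidence interval

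*SAP*

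**What the plan says.** SAP 2.3.2 lists the endpoint as "Change in Borg Dyspnoea Scale (mBDS) from baseline to Day 7; Day 28; Day 60". In SAP 5.2.1 the Borg hypothesis is written for means that "represent the scale shift through day 7, 28, and 60 for Ampion and Placebo after randomization", yet the difference between arms "with respect to the percent change from baseline at day 7, 28, and 60 will be tested utilizing a Wilcoxon rank-sum test". The same test is planned for the FDA 14-symptom score (5.2.1), oxygen saturation and the six-minute walk (5.2.2), and SF-36, fatigue and sleep (5.2.3), which makes seven endpoints. For each, "an exploratory repeated measures analysis of variance will be performed with terms for treatment, time and the interaction between the two", to look at time trends.

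On order, SAP 5.2 states: "In order to preserve the alpha level these will be tested hierarchically in the order presented here". Borg comes second, after the FDA score. On population, SAP 6.2.2 states: "All efficacy analyses will be performed in the ITT population". It defines that population as all randomized patients.

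On the scale, SAP 15.2 says that "it starts at number 0 where you are breathing is causing you no difficulty at all". Protocol 4.4, inclusion criterion 3, asks for at least two symptoms scored 2 or higher from this list: "cough, sore throat, runny/stuffy nose, shortness of breath (difficulties breathing), tightness of chest, low exercise tolerance".

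SAP 7 provides descriptive statistics by arm and pooled, with a 95% confidence interval on change from baseline. Protocol 9.4.2 gives estimation of the treatment effect as the purpose of the efficacy evaluation and describes tabulation by arm.

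**The concern.** Percent change divides by the baseline value, so a participant who starts at Borg 0 has no value to rank. Cough plus sore throat is enough for entry, and no minimum Borg score is set, so such participants can be enrolled. The test would then describe only those with some breathlessness at baseline. A participant who goes from no breathlessness to some while inhaling the study product would not count in the comparison of breathlessness.

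The second gap concerns what the trial delivers. It is meant to inform further development and is not powered. With 15 per arm, an estimated difference and its interval tell the sponsor more than a p-value, and the SAP does not ask for that interval.

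**Working it through.** **1. The undefined value.** Percent change = 100 × (follow-up − baseline) / baseline. From 0 to 0 this is 0/0; from 0 to 2 it divides by zero. Small baselines also stretch the ranks: the same 2-point worsening is +400% from 0.5, +67% from 3 and +33% from 6.

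**2. Is there a rule?** SAP 6.3 and protocol 9.5 cover adverse event data. SAP 13 covers dates of adverse events and medications. Neither covers an efficacy value.

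**3. Which endpoints?** Borg clearly. An FDA total of 0 is less likely but not excluded: chest tightness and low exercise tolerance qualify for entry and are not among the 14 items.

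**4. Does the repeated-measures analysis fill the gap?** Its terms are treatment, time and their interaction, with no baseline covariate, and its response variable is not stated. If that is percent change, the same participants drop out; if it is the visit score, they stay.

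**5. How many are lost?** The documents give no share with Borg 0, so p is assumed. Expected loss = 30p; chance of losing at least one = 1 − (1 − p)^30.

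| p | expected loss | at least one lost |
|---|---|---|
| 3% | 0.9 | 60% |
| 8% | 2.4 | 92% |
| 19% | 5.7 | 99.8% |

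**6. What does it do to power?** The plan states no power, effect size or SD, so there is no figure to reproduce and every input here is assumed. Simulation: 15 per arm, two-sided 5%, 3000 runs per cell, Borg grid 0, 0.5, 1, 2 to 10, baseline mean 4, 3 or 2 with SD 2 (giving 3, 8 or 19% at zero). Zeros are dropped for the planned test only.

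- Additive model: both arms fall by 0.3, active by a further 1.5 points; columns are correlation 0.3/0.5/0.7.
- Proportional model: follow-up = 0.9 × baseline × lognormal error, 35% lower on active; columns are log-error SD 0.3/0.5/0.7.

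| zeros | additive: planned | additive: ANCOVA | proportional: planned | proportional: ANCOVA |
|---|---|---|---|---|
| 3% | 41/51/69 | 53/60/75 | 91/53/32 | 89/49/31 |
| 8% | 39/48/62 | 51/56/71 | 87/50/30 | 85/45/28 |
| 19% | 34/43/56 | 46/52/64 | 77/45/27 | 73/38/22 |

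ANCOVA minus planned, additive: +12/+9/+6, +12/+8/+9, +12/+9/+8, so 6 to 12 points higher. Proportional: −2/−4/−1, −2/−5/−2, −4/−7/−5, so 1 to 7 points lower.

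**7. How much of the additive gain comes from the zeros?** Comparing ANCOVA with the zero-baseline participants kept and dropped gives about 1–2 points at 3% zeros, 1–5 at 8% and 5–7 at 19%. The rest comes from baseline adjustment and the choice of test.

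**8. FDA score** (assumed mean 14, SD 5, baseline at least 4, so no zeros). Additive 5 points: 63/77/92 planned, 77/86/95 ANCOVA, a gain of 14/9/3. Proportional 35%: 96/59/34 planned, 93/54/31 ANCOVA, a loss of 3/5/3.

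**9. Type I error and precision.** Across the simulations, type I error was 3.4–5.4% for the planned test and about 4–6.5% for ANCOVA, near nominal within simulation error. The 95% CI half-width for the adjusted Borg difference was about 0.6 to 1.7 points.

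**The case against.** The endpoints are exploratory, the trial is unpowered, and the primary safety endpoint is untouched. Zeros may be rare, particularly if the Borg rating analysed is the one taken after the walk. All of this stands and limits the weight of the point. But the SAP chose formal tests in a fixed order, so the tested variable should be computable for everyone in the stated population. A rule set before unblinding avoids a choice made after it.

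It can also be said that the point difference between arms follows from the by-arm means by subtraction, and that protocol 9.4.2 itself describes by-arm presentation. That is correct: what is missing is the confidence interval for the difference.

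Some stronger readings are tempting and do not hold:

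- A reader might infer that leaving out baseline adjustment is an error. It is not. An unadjusted rank test is valid in a randomized trial, and adjustment is a matter of efficiency.
- A reader might take the 6 to 12 points as the cost of the zeros, or as a general advantage of ANCOVA. At low zero rates most of the gap has other causes. Under a proportional effect the sign reverses, and the documents give no basis for choosing between the models.
- A reader might extend the inconsistency to SAP 5.2.2 and 5.2.3. There the hypotheses already concern a percentage shift, which matches the test, and no undefined value has been shown.

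**Conclusion.** The point holds for two gaps. First, the Borg test has no rule for a baseline of 0, and the plan as written removes those participants from an analysis described as intent-to-treat; the FDA score carries the same risk at lower likelihood. Second, none of the seven endpoints has a planned between-arm difference with a confidence interval.

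Both follow from the documents alone. The sizes do not: the share at zero, the effect model and the SDs are all assumed. No inflation of type I error by the planned test and no general power gain from ANCOVA are claimed. This should be fixed because it is cheap and makes the results easier to interpret; it does not threaten the trial's primary purpose.

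**What to change.** **Borg and FDA score (SAP 5.2.1).** The hypotheses there already concern a score or scale shift. Compare arms at each visit on absolute change by ANCOVA with baseline as covariate, and report the adjusted difference with its 95% CI. Use rank ANCOVA as a sensitivity analysis. Keep percent change as a descriptive summary where baseline is above 0. Unadjusted absolute change alone is not a good substitute: on Borg it had 5–11 points less power than the planned test under the additive model and 3–16 less under the proportional one.

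**If the percent-change Wilcoxon is kept.** State a baseline-0 rule before unblinding, for example 0 to 0 ranked as no change and 0 to above 0 ranked as worst, and add a between-arm difference with 95% CI. In the simulations that rule had 0 to 6 points less power than dropping the zeros.

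**SAP 5.2.2 and 5.2.3.** Add a between-arm difference with 95% CI. Baseline-adjusted ANCOVA is optional; if adopted, the percentage-shift hypotheses must be reworded to match.

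**Clarify.** Name the Borg rating analysed (stand-alone, before or after the walk) and the response variable of the repeated-measures analysis. Participants with no post-baseline value need a separate rule under any option.

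**Cost.** SAP wording and a few lines of code; baseline is already collected for every scale. If the true effect is proportional, ANCOVA may lose about 1–7 points of power on Borg and 3–5 on the FDA score.

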6.3 MISSING DATA

All data collected under this study protocol will be included in the assessment of patient safety. Missing or incomplete AE data will assume greatest relationship to study drug and/or severity.

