7 SUMMARY OF STUDY DATA

Data will be summarized by each treatment arm and by pooled Control and Ampion arms. Descriptive statistics on continuous variables will include mean, standard deviation, median, 25th, and 75th percentiles, and range. Change from baseline will include a 95% confidence interval. Categorical variables will be summarized using frequency counts and percentages. Data listings of individual subject's data will be provided.

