13.1 IMPUTATION RULES FOR PARTIAL OR MISSING STOP DATES

If the month and year are present, impute the last day of the month. If only the year is present, impute December 31 of that year. If the stop date is entirely missing, assume the event or medication is ongoing. If a partial or complete stop date is present and the ‘ongoing’ or ‘continuing’ box is checked, then it will be assumed that the AE or concomitant medication stopped and the stop date will be imputed, if partial.

		Stop Date						
		Complete: yyyymmdd		Partial: yyyymm		Partial: yyyy		Missing
Start Date		<1 st Dose	≥1 st Dose	<1 st Dose yyyymm	≥1 st Dose yyyymm	<1 st Dose yyyy	≥1 st Dose yyyy	
Partial: yyyymm	=1 st Dose yyyymm	2	1	2	1	N/A	1	1
	≠ 1 st Dose yyyymm		2		2	2	2	2
Partial: yyyy	=1 st Dose yyyy	3	1	3	1	N/A	1	1
	≠ 1 st Dose yyyy		3		3	3	3	3
Missing		4	1	4	1	4	1	1

1 = Impute the date of first dose

2 = Impute the first of the month

3 = Impute January 1 of the year

4 = Impute January 1 of the stop year

Note: For subjects who were never treated (first dose date is missing), partial start dates will be set to the first day of the partial month.

Note: If the start date imputation leads to a start date that is after the stop date, then do not impute the start date.

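### The exploratory time-trend ANOVA in PROC GLM with REPEATED silently becomes a complete-case analysis, and no rule covers missing efficacy values; a mixed model is a cheap improvement

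*SAP*

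**What the plan says.** SAP 5.2.1 compares the arms on the symptom questionnaire and the Borg scale with Wilcoxon tests on percent change at Days 7, 28 and 60. It then adds a second analysis: "To assess any potential time trends an exploratory repeated measures analysis of variance will be performed", with treatment, time and interaction terms. The software is fixed: "This will be done utilizing PROC GLM with the REPEATED option". SAP 5.2.2 repeats this for oxygen saturation and the six-minute walk, and SAP 5.2.3 for SF-36, fatigue and sleep. That makes seven endpoints. The response variable of the ANOVA is not named.

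On population, SAP 6.2.2 states: "All efficacy analyses will be performed in the ITT population". On missing data, SAP 6.3 (like Protocol 9.5) addresses adverse events: "Missing or incomplete AE data will assume greatest relationship to study drug and/or severity". SAP 13.1 deals with adverse-event and medication dates, for example "If the stop date is entirely missing, assume the event or medication is ongoing". No section says what happens to a missing efficacy score.

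Missed visits are foreseen. SAP 7.1 summarises attendance, missed visits, discontinuations and loss to follow-up. Protocol 9.3 reports the count of non-missing observations for continuous variables.

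**The concern.** PROC GLM with REPEATED takes one row per participant, with the visits as separate dependent variables, and excludes a row if any of them is missing. One missed visit therefore removes that participant's other visits from the model. The treatment-by-time results for seven endpoints could rest on fewer than the 30 randomized participants, and on a different set for each endpoint, with nothing in the output to say so.

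Two gaps could enlarge the loss:

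- **Response scale.** If the ANOVA follows the percent change used for the Wilcoxon tests, a Borg baseline of 0 gives an undefined value. The scale allows it: "it starts at number 0 where you are breathing is causing you no difficulty at all". Entry does not prevent it. Protocol 4.4 asks for "Experiencing at least two COVID-19 respiratory symptoms with a score of two or higher" from a list of six, so cough and sore throat are enough and dyspnoea is not required.
- **Interim.** SAP 6.1 plans efficacy analyses once everyone has completed Day 28. A three-visit GLM run then would delete everyone not yet at Day 60, even with perfect attendance.

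**Working it through.** **Inputs.** 30 participants, 15 per arm (SAP 4); three post-baseline visits (SAP 2.3.2). The documents state no missing rate, SD, correlation or expected analysed number, so there is no planned figure to reproduce. Every rate below is an assumption.

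**Participants analysed.** Let q be the share of visits missed.

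| q | GLM, independent misses: 30(1-q)^3 | Mixed model, independent misses: 30(1-q^3) | Either model, misses fully clustered: 30(1-q) |
|---|---|---|---|
| 5% | 25.7 | 30.0 | 28.5 |
| 10% | 21.9 | 30.0 | 27.0 |
| 15% | 18.4 | 29.9 | 25.5 |

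If baseline were entered as a fourth repeated level, GLM would keep 30(1-q)^4 = 24.4, 19.7 or 15.7. With 20% monotone dropout by Day 60 it keeps 30 x 0.8 = 24.

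**Precision.** Head counts overstate the gain for a time contrast. At q = 10%, sqrt(30/21.9) = 1.17, but a participant seen only once adds little to Day 60 minus Day 7. The table gives the ratio of standard errors, complete-case over all available data. It uses generalised least squares with known equal correlation of 0.4, 0.6 or 0.8, 15 per arm, and 4,000 missing patterns per setting.

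| Pattern | Day 60 minus Day 7 | Average over visits |
|---|---|---|
| 5% independent | 1.044-1.048 | 1.073-1.084 |
| 10% independent | 1.092-1.104 | 1.157-1.178 |
| 15% independent | 1.147-1.170 | 1.257-1.289 |
| 20% monotone dropout | 1.022-1.037 | 1.090-1.115 |

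Fitting the mixed model itself (REML, unstructured covariance, baseline term, Kenward-Roger, 600 trials per setting) gave time-contrast ratios of 1.03-1.07, 1.08-1.13, 1.13-1.18 and 1.02-1.03.

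**Bias.** Assume dropout depends on the previous outcome in both arms (about 22 completers) and a constant effect of -0.5 SD. Complete-case bias is then 0.02-0.05 SD for the time contrast, against a standard error of 0.27-0.45 SD, and 0.07-0.09 SD for the average. If the effect grows from 0 to -0.5 SD, the biases are 0.00 and 0.01 SD. The mixed model's bias stayed within 0.02 SD for both contrasts.

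**Small-sample behaviour.** With 10% of visits missed independently, correlation 0.6, equal visit variances and 2,500 trials per setting, type I error for the time contrast (nominal 5%) was 5.0-5.1% for the unstructured model. Compound symmetry gave 8.5% when the truth was AR(1). Uncorrected sandwich errors gave 7.2-7.6%. The unstructured fit converged in 4,998 of 5,000 trials.

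**Fallback covariance.** Plain Toeplitz pools the visit variances. With assumed SDs of 1, 1.25 and 1.5, the pooled SD is sqrt((1 + 1.5625 + 2.25)/3) = 1.27. Since 1.27/1.5 = 0.84, the Day 60 standard error is about 16% too small. In simulation with complete data and AR(1) correlation 0.6, plain Toeplitz gave 5.0% type I error for the time contrast but 9.4% for the Day 60 difference; unstructured gave 5.1% at Day 60.

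**Interim.** 60 - 28 = 32 days nominally. With the 3-day visit windows the gap runs from 57 - 31 = 26 to 63 - 25 = 38 days.

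**The case against.** The case for leaving this alone is substantial. The model is exploratory and no stated decision rests on it. Its purpose is time trends, where the gain is smallest: 2-4% under monotone dropout and nil under full clustering. In simulation under outcome-dependent dropout, the standard-error ratio was 0.98-1.02. Gains of 9-17% need 10-15% of visits missed independently, which nothing in the documents supports or excludes. All of this stands and limits the size of the point. It does not supply the missing rule.

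The scale argument also has limits. The SAP states percent change for the Wilcoxon tests; for the ANOVA it is only a possibility. Five of the seven endpoints are defined there as a percentage shift. The walk-test procedure records Borg ratings before and after exertion, and the SAP does not say which is the endpoint; zeros may be rarer after exertion. No document gives the share with a baseline of 0. These points also stand.

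A reader might infer that GLM contradicts the ITT definition. It does not. SAP 6.2.2 says who belongs to the population and under which arm; it is silent on missing values. What is absent is a missing-data rule. A reader might also infer that a subset is being concealed. That is too strong, because attendance and non-missing counts are reported elsewhere. Only the model's own complete-case status and n are unreported.

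**Conclusion.** The point holds as a cheap improvement. SAP 5.2.1 to 5.2.3 choose a procedure that deletes partly observed participants, and neither document has a rule for missing efficacy values. Under assumed independent misses of 5%, 10% or 15%, about 26, 22 or 18 of 30 remain, and the time-contrast standard error is about 4-5%, 9-10% or 15-17% larger than it need be. There is no gain from the switch if misses cluster fully or do not occur.

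It would be wrong to infer that the formal efficacy tests or the safety result are compromised. The per-visit Wilcoxon tests lose only participants missing that visit, and the primary adverse-event endpoint does not use this model. Nor do the bias figures show a misleading time trend: the bias is small against its standard error. The precision figures rest on equal correlation between visits and equal visit variances.

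**What to change.** **Model.** In SAP 5.2.1 to 5.2.3 replace PROC GLM REPEATED with PROC MIXED: treatment, time, treatment-by-time and baseline value; visits repeated within participant; unstructured covariance; Kenward-Roger degrees of freedom. Include every randomized participant with a baseline and at least one post-baseline value. Report the model's n and the n per visit. If the fit does not converge, use heterogeneous Toeplitz with Kenward-Roger, which allows unequal visit variances. It was not itself simulated here, and the fallback should rarely be needed.

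**Scale.** State the response. I recommend absolute change. The SAP does not name it, but it is consistent with endpoints worded as change (SAP 2.3.2) and with SAP 7: "Change from baseline will include a 95% confidence interval". It also avoids undefined values at a Borg baseline of 0.

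**Missing data.** Add to SAP 6.3 that efficacy analyses use observed values without imputation and that the mixed model assumes missing at random.

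**Interim.** If the model is run at Day 28, state that only Days 7 and 28 enter, because participants enrolled within nominally 32 days (about 26-38 with the visit windows) of the last enrolment will not have reached Day 60.

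**Cost.** Wording in three subsections, an addition to 6.3 and routine code. Visits, data collection, sample size, the Wilcoxon tests and their order are unchanged. There are two downsides to disclose. The model would sit on a different scale from the percent-change Wilcoxon tests, whose own zero-baseline problem is not fixed here. It also relies on missing at random. The change should be made before unblinding, since SAP 2 treats analyses added after data review as post hoc.

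**Minimum alternative.** Keep PROC GLM, label it complete-case, state the response scale and report n for each endpoint.
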